B1.2 Cannabis is the most commonly used drug by PLWH.⁷ In the US, most states have legalized either medicinal or recreational cannabis.⁸ Cannabis use is disproportionately higher among PLWH. The estimated prevalence of cannabis use in PLWH ranges from 20 -60%,⁹ with nearly half reporting regular use (operationalized as ≥ 4 times/week).¹⁰ Many PLWH report pre-infection cannabis use that continues after seroconversion to ameliorate HIV symptoms and/or side effects associated with treatment (e.g. neuropathic pain, nausea, mood problems, appetite, and weight loss).¹¹⁻¹³ While cannabis use disorder (CUD), as defined by the Diagnostic and Statistical Manual of Mental Disorders 5th Edition (DSM-5),¹⁴⁻¹⁶ has been linked to worse cART adherence¹⁷ and an increased risk for becoming infected,¹⁸ this may not be the entire story. Central to the current proposal, a previous analysis revealed that progressive cognitive worsening among PLWH on cART was evident only in individuals with substance use (e.g. cannabis).¹⁹

B1.3 Cognitive dysfunction persists in PLWH despite cART. Approximately 40% (12%–99%) of PLWH exhibit neurocognitive symptoms despite sustained viral suppression with cART.⁴⁰ Chronic cognitive difficulties following cART result from a combination of risk factors, including irreversible neurologic injury prior to treatment onset, persistent HIV reservoirs, immune activation, and inflammation.²⁰⁻²⁵ *A central tenet of the current proposal is that these mechanisms are potentiated by regular use of drugs of abuse, such as cannabis. Confirmation of this hypothesis would be clinically significant because cannabis use is a modifiable risk factor that can be addressed through clinical interventions, but rigorous science is required to guide policy and clinical practice.*^{17, 26}

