(3) Accelerates scientific discoveries in HIV/AIDS and substance use research by enhancing the pace of translational processes through team science. This proposal brings together scientists and clinicians with expertise in substance use and HIV. Our multi-disciplinary team has been at the forefront of evaluating peripheral and brain inflammation, quantifying cannabis use, and utilizing cognitive measures and neuroimaging methods in PLWH and HIV- controls. The team is composed of experts in neuroimaging ([name]), blood and cerebrospinal fluid (CSF) inflammatory markers ([name]), neurobehavioral phenotyping of HIV ([name]), cannabis use ([name]), and statistics ([name]). Each investigator has an ongoing record of accomplishments and has helped advance their respective field. The team has continued to have weekly meetings via Zoom despite COVID-19 and crossing multiple time zones. A multi-PI plan is in place for Drs. [name] and [name], who have complementary and integrated expertise and have extensively worked together.

Using a cross sectional study design, we will acquire phenotype data from peripheral and brain markers of immune function (e.g. CD4/CD8 ratio, monocyte subpopulations, plasma sCD14 and sCD163, CSF MCP-1 and neopterin, and DBSI cellularity), brain structure (volumetrics), and cognition from four groups: virally controlled (< 20 copies/mL) PLWH on cART with regular cannabis use (PLWH, CB+; n = 80), virally controlled (< 20 copies/mL) PLWH with no cannabis use (PLWH, CB-; n = 80), HIV- controls with regular cannabis use (CON, CB+; n = 80) and HIV- controls with no cannabis use (CON, CB-; n = 80)

C Study Objectives

C1 Primary Aim

Specific Aim 1: Cannabis use increases peripheral and brain immune activation and inflammation indices in virally controlled PLWH on cART.

Hypothesis 1a: Peripheral and brain immune activity (e.g. inversion of CD4/CD8 ratio, elevated sCD14, sCD163, monocyte subpopulations, MCP-1, neopterin, and cellularity) are elevated in PLWH, CB+ compared to other groups (PLWH, CB-; CON, CB+; and CON, CB-).

Hypothesis 1b: Peripheral and brain immune indices (e.g. CD4/CD8 ratio, sCD14, sCD163, monocyte subpopulations, MCP-1, neopterin, and cellularity) will be moderated by concentrations of THC and CBD metabolites.

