Serious adverse events may be reported to the IRB within the timeline outlined in their policies and procedures. The stopping criteria and guidelines to be used for this protocol may include the following: 1) The study may be stopped if there is clear evidence of harm or harmful side effects of the procedures used in this protocol; 2) In the event that a serious adverse event (SAE) occurs that increases the risks to participants, the study may be stopped and an investigation be conducted and a findings report generated by the PI; 3) Should there be an SAE or adverse event (AE) that occurs at a frequency greater than 5%, it will be added to the consent document, if not already addressed, and enrollment may be halted while a determination is made regarding the potential risks to participants. The risks of the study are low, however, the PI and study physicians as well as the WUSTL IRB will review safety material and the protocol at least annually.

F Statistical Plan

Considerations for data science methods: Continuous variables will be transformed as needed prior to analyses to improve normality and linearity of the relationship to the designated outcome variable. Raw NP tests that measure time on a task will use an inverse transformation $f(t) = 1/t$, measuring the speed of task completion; for other tests an empirical normal quantile transformation and normative corrections for demographics will be considered, which will lead to scale scores and z-scores. NP global and sub-domain values are likely to be normally distributed, which will allow for multivariable linear regression. The distributions of depression, apathy, and HRQoL scores are likely to be right-skewed and over-dispersed; therefore, negative binomial regression may be considered for analyses. All statistical tests will be two-sided, with significance declared at the $p < 0.05$ level (unless otherwise stated). In addition to hypothesis testing, 95% confidence intervals (95%CI) will be determined for effect sizes of interest. Sex will be investigated as a potential predictor of interest for each hypothesis and analysis. In exploratory analyses, correction for multiple comparisons will preserve the false discovery rate (FDR) at the 0.05 level.

Demographics: Demographic, medical, psychosocial, and lab characteristics of participants will be summarized using N (%) for categorical variables, and mean, standard deviation, and range for numeric variables.

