Aim 1: *Hypothesis 1a.* The effect of regular cannabis use on peripheral and brain inflammatory markers (primary response: composite markers; secondary: individual inflammatory markers) will be analyzed using linear models (analysis of covariance), including as predictors cannabis status, HIV, and their interaction. If an interaction effect between cannabis and HIV status is not significant, additive effects will be evaluated. Demographic factors such as Wide Range Achievement Test (WRAT)-4, sex, and age will be examined as explanatory variables and incorporated into the final models if significant at $p < 0.20$ on backward model selection. Secondary marker analyses will control for multiple tests by keeping the overall FDR at level $\alpha = 0.05$. The effect of cannabis on peripheral and brain inflammatory markers among PLWH and HIV- controls will be reported based on these models using a 95%CI. In the absence of a HIV-by-cannabis interaction, the additive effects of cannabis and HIV are of primary interest. If an interaction is present, then the primary comparison will be between CB+ and CB- groups among PLWH (at $\alpha = 0.05$). Secondary analyses will compare the PLWH, CB+ to the other two groups (at familywise error rate $\alpha = 0.05$).

Hypothesis 1b. The relationship between cannabis exposure (KMSK and urine analysis of cannabis metabolites) and peripheral and brain immune activity markers (primary response: composite markers; secondary: individual markers, possibly log-transformed, as noted above) will be analyzed among regular cannabis users using linear models. Demographic factors such as the WRAT-4, sex, and age will be examined as explanatory variables and incorporated into the final models if significant at $p < 0.20$ on backward model selection. In addition to linear effects, non-linear cannabis effects will also be considered, including quadratic effects and smooth effects fitted via generalized additive models. Possible interactive effects between cannabis exposure levels and HIV will also be examined.

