Hypothesis 1c: Data-driven feature selection methods⁹²⁻⁹⁵ will be performed to identify novel mechanisms and associations between regular cannabis use and peripheral and brain immune activity measures that differentiate HIV serostatus from cannabis use. The analysis will yield a subset of biomarkers that are most indicative of the effects of cannabis on brain immune activation and inflammation, while excluding irrelevant and redundant biomarkers. Continuous variables will be normalized to zero mean and unit variance. Features will be scaled independently to a common interval to ensure that features with higher magnitudes are not given preference during training. All analysis will be conducted with 10-fold cross validation with 10 repeats to ensure the reliability of the results.⁹⁶ Individual models will be trained with a categorical cross entropy loss function, and evaluated based on sensitivity, specificity, and receiver operator curve (ROC) area under the curve (AUC) F1 analyses. Models will be compared using mean misclassification rate and Bayesian information criteria.⁹⁷ Analysis will be performed in common programming languages and packages (MATLAB, Python, and R).

Power Analysis for Aim 1:

Hypothesis 1a. With the proposed sample size of $n = 320$, we have $\geq 80\%$ statistical power to detect an HIV-by-cannabis group interaction effect (difference-in-differences) corresponding to Cohen's $d = 0.634$ and $d = 0.758$, for peripheral and brain immune activation markers, respectively. In absence of this interaction, we have 80% power to detect a cannabis effect among PLWH of Cohen's $d = 0.446$ for peripheral and $d = 0.533$ for brain immune activity markers. In secondary analyses, we have 80% power to detect a difference between PLWH, CB+ group and either the CON, CB+ or CON, CB- groups of Cohen's $d = 0.491$ or $d = 0.587$ (periphery/brain respectively), Holm-Bonferroni corrected. These calculations assume a 70% LP completion rate, per our past experience. This sample size is sufficient for the planned analyses. In our preliminary analyses we found an effect size of $d = 0.52$ for the PLWH comparison of CB+ and CB- (Figure 3A).

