Hypothesis 2b: The effect of THC and CBD concentrations among cannabis users on NP and brain volumetrics will be analyzed using linear models. Demographic factors such as the WRAT-4, sex, and age will be examined as explanatory variables and will be incorporated into the final models if significant at $p<0.20$ in backward model selection. Possible non-linear cannabis effects will be explored, including quadratic effects and smooth effects fitted via generalized additive models. A possible interaction between cannabis exposure levels and HIV will also be examined.

Hypothesis 2c: Data-driven feature selection methods⁹²⁻⁹⁵ will be performed to reveal highly dimensional mechanisms and associations between cannabis use and brain integrity (cognition and volumetrics) that differentiate HIV serostatus from regular cannabis use. The analysis will yield a subset of biomarkers that are most indicative of the effects of cannabis on brain integrity (NP and volumetrics), while excluding irrelevant and redundant biomarkers. Continuous variables will be normalized to zero mean and unit variance. Features will be scaled independently to a common interval to ensure that features with higher magnitudes are not given preference during training. All analysis will be conducted with 10-fold cross validation with 10 repeats to ensure the reliability of the results.⁹⁶ Individual models will be trained with a categorical cross entropy loss function, and evaluated based on sensitivity, specificity, and receiver operator curve (ROC) area under the curve (AUC) F1 analyses. Models will be compared using the mean misclassification rate and Bayesian information criteria.⁹⁷ All analysis will be performed in common programming languages and packages (MATLAB, Python, and R).

Power Analysis for Aim 2:

Hypothesis 2a: With the proposed sample size of $n=320$ we have $\geq 80\%$ statistical power to detect additive effects of HIV status and cannabis use on NP and volumetrics outcomes corresponding to Cohen's $d=0.314$ each. This effect size is consistent with those determined in our preliminary data (Cohen's $d=0.584$ for cannabis and $d=0.418$ for HIV in *Figure 5*).

Hypothesis 2b: We have $\geq 80\%$ power to detect an effect of cannabis exposure among cannabis users on NP or volumetric outcomes corresponding to $R^2=0.047$ proportion of variance explained, or equivalently

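### Hypotheses 1b and 2b pool HIV+ and HIV- cannabis users without specifying an HIV main effect, so a serostatus difference can appear as, or hide, a THC/CBD association

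*Combined protocol and SAP*

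**What the plan says.** Section F, Hypothesis 1b: the relation between exposure (KMSK and urine metabolites) and the immune composites "will be analyzed among regular cannabis users using linear models". The covariates are demographic, with WRAT-4, sex and age as examples, and are kept if p < 0.20 on backward selection. HIV is mentioned once, at the end: "Possible interactive effects between cannabis exposure levels and HIV will also be examined".

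Hypothesis 2b has the same structure: "The effect of THC and CBD concentrations among cannabis users on NP and brain volumetrics will be analyzed using linear models". It uses the same covariate rule and again closes with a possible exposure-by-HIV interaction.

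Hypothesis 1a, just before 1b, is written differently. It names cannabis status, HIV and their interaction as predictors, and it moves to additive effects if the interaction is not significant. Hypotheses 1b and 2b contain neither statement.

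The Cannabis paragraph of Section F describes the exposure analyses as exploratory. Even so, 1b is a numbered hypothesis under the Primary Aim and 2b under the Secondary Aim, and each has its own power statement.

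**The concern.** A pooled exposure-response slope mixes two things: the slope within each serostatus group, and the line joining the two group means. The second part is confounding by HIV. It arises when HIV shifts the outcome and the two groups of users also differ in exposure.

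The first condition is one the plan itself expects. Hypothesis 1a predicts higher immune activity in HIV+ users than in HIV- users, and those are the two groups pooled here. The peripheral composite includes the CD4/CD8 ratio. The Aim 2 power section cites a preliminary HIV effect of d = 0.418. The second condition is possible but undocumented: controls are matched on demographics as far as possible, and nothing balances exposure level by serostatus.

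The interaction check does not reliably protect the result. For the primary cognitive outcomes, the plan expects additive and not interactive effects of HIV and cannabis. A non-significant interaction would then be dropped, and nothing says that HIV stays in the model. At stake is whether a reported THC or CBD association, or its absence, reflects exposure or serostatus.

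**Working it through.** **1. Are the users pooled?** Inputs: 80 HIV+ and 80 HIV- regular users (end of Section B1); two-sided alpha 0.05 (Section F); 80% power; and for brain markers "These calculations assume a 70% LP completion rate, per our past experience", so 0.70 × 160 = 112. The stated detectable correlations are 0.219 (R² = 0.047) for peripheral markers and for 2b, and 0.262 (R² = 0.069) for brain markers.

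Fisher's z gives r = tanh[(1.960 + 0.842)/√(n − 3)]:

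- n = 160: tanh(2.802/12.53) = 0.220
- n = 112: tanh(2.802/10.44) = 0.262
- n = 80 (one serostatus only): 0.309
- n = 56 (one serostatus only, with LP): 0.367

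Simulated power is 80.0% at r = 0.219 with n = 160, and 80.2% at r = 0.262 with n = 112. The plan's figures match only the pooled samples.

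**2. How large an apparent correlation does serostatus create?** Take two equal groups with no association inside either. Let HIV+ and HIV- users differ by dy SD in outcome and dx SD in exposure. The pooled correlation is

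r = [(dx/2)/√(1 + dx²/4)] × [(dy/2)/√(1 + dy²/4)]

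- dy = 0.418, dx = 0.5: 0.243 × 0.205 = 0.050
- dy = 0.418, dx = 0.8: 0.371 × 0.205 = 0.076
- dy = 1.0, dx = 0.5: 0.243 × 0.447 = 0.108
- dy = 1.0, dx = 0.8: 0.371 × 0.447 = 0.166

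These compare with a detectable r of 0.219. If exposure differs in the opposite direction, the sign reverses and a real association can be masked.

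**3. False-positive rate of the exposure test without an HIV term** (10,000 simulated studies per cell, nominal 5%):

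| Setting | dx = 0 | 0.3 | 0.5 | 0.8 |
|---|---|---|---|---|
| n = 160, dy = 0.418 (relevant to 2b) | 5.1% | 6.4% | 9.3% | 15.9% |
| n = 160, dy = 1.0 (peripheral, assumed) | 5.3% | 13.1% | 27.3% | 57.2% |
| n = 112, dy = 1.0 (brain, assumed) | 4.8% | 11.2% | 20.8% | 43.0% |

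Simulation error is up to about one percentage point. With an HIV main effect in the model, the rate is 4.5% to 5.5% in every scenario.

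Sources: dy = 0.418 is the preliminary HIV effect in the Aim 2 power section, cited for cognition and volumes; I assume that it carries over to users. dy = 1.0 and every dx are assumptions.

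**4. What does the HIV term cost in power?** Use the noncentral F test with noncentrality n × f². At R² = 0.047 and n = 160, f² = 0.047/0.953 = 0.0493 and the noncentrality is 7.89.

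- HIV unrelated to outcome and exposure: 79.7% with or without the term.
- HIV effect d = 0.418: HIV explains 0.209²/(1 + 0.209²) = 0.042 of the variance, f² = 0.047/0.911 = 0.0516, power 81.5%.
- Exposure differs by 0.5 SD and HIV does not affect the outcome: noncentrality is multiplied by 1 − 0.059, power 77.3%.
- The same with a 0.8 SD difference: multiplied by 1 − 0.138, power 73.6%.

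**The case against.** **HIV is unspecified, not excluded.** A reader might infer that the plan rules out an HIV main effect. It does not. A conventional interaction model carries the main effect, so an analyst might well include it. That stands as a limit on the wording. It does not remove the point, because the interaction is an additional, possible examination, the covariate list is demographic, and no additive fallback is given.

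**Prevalence is not dose.** A reader might also take Section B1.2, "Cannabis use is disproportionately higher among PLWH", as evidence that HIV+ users have higher exposure. The figures that follow concern how many people use cannabis and how many use it regularly. Both groups here are selected as regular users, and the remark on symptom relief gives a reason for use, not an amount. This objection stands: no document figure supports any particular dx.

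**The large rates rest on assumed shifts.** The CD4/CD8 ratio is one of six markers in the first principal component, and its loading is unknown. A strong HIV effect on that ratio therefore does not establish a 1.0 SD shift in the composite. For 2b the induced correlation, 0.05 to 0.08, is well below the detectable 0.219.

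**The analyses are labelled exploratory.** The main cannabis comparison is users against non-users, with HIV in the model. This tempers the severity. But the label does not remove confounding, nor does control of the false discovery rate, and both hypotheses are numbered and separately powered.

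**Conclusion.** The concern holds as an omission in specification. Pooling is confirmed by the text and by the plan's own power figures, and no HIV main effect is stated for the main exposure test in 1b or 2b. Run as written, that test can be confounded by serostatus.

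The size is conditional on HIV shifting the outcome and on exposure differing between HIV+ and HIV- users. If exposure does not differ, there is no inflation. At the documents' only HIV effect, which bears on 2b, the false-positive rate is modest: about 6% to 16% for exposure shifts of 0.3 to 0.8 SD. It becomes serious for the immune composites only if HIV moves them by something like the assumed 1.0 SD: for exposure shifts of 0.5 to 0.8 SD, about 27% to 57% for peripheral and 21% to 43% for brain markers.

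The documents do not support a claim that a THC/CBD finding from this study would probably be spurious. The confidence is in the omission and in the remedy, not in the magnitude of the bias.

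**What to change.** State in Hypotheses 1b and 2b that HIV status enters every exposure model as a main effect, exempt from the p < 0.20 backward selection, and that it stays in when the interaction is not significant. This should cover the quadratic and smooth-effect models too. Report the common within-serostatus slope as the main result, with the exposure-by-HIV interaction and the slopes for HIV+ and HIV- users beside it. A table of exposure level by serostatus among users would show how much the adjustment matters.

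The cost is a sentence or two in each hypothesis and one degree of freedom, using a variable already collected. Power rises slightly if HIV affects the outcome but exposure is balanced. It falls if exposure differs and HIV has no effect on the outcome: from 79.7% to 77.3% at a 0.5 SD difference, and to 73.6% at 0.8 SD. The sample size does not change.

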Hypothesis 1b. We have $\geq 80\%$ power to detect an association between cannabis exposure and peripheral immune activity markers explaining $R^2 = 0.047$ or more of the variance in the response, corresponding to a small Pearson correlation coefficient of $r = 0.219$ or higher. This effect size is achievable. In our preliminary data, we observed higher correlation levels (Figure 4). For brain inflammatory activity

markers the corresponding values are $R^2=0.069$, $r=0.262$. The power calculations used statistical software (G*Power).

Hypothesis 1c: Sample size determination for classifier development aims will seek to improve predictor accuracy and significance.⁹⁸ Sample size determinations were conducted using proposed published methods. Training and testing errors of cross validated progressively sampled models will be assumed to follow power laws and will be evaluated based on asymptotic error value convergence to identify appropriate sample sizes.^{99, 100} Results will be optimized based on nonlinear weighted least squares fitting.¹⁰¹ Cross validated model performance will be compared using empirical and uniform priors to determine the effect of balanced classes.¹⁰² Cross validation of data with randomly permuted labels will be used to identify the significance of model results.¹⁰³

Aim 2:

Hypothesis 2a: The effect of cannabis and HIV on cognition will be quantified through linear models, similar to those discussed under Hypothesis 1a, adjusting for confounding factors. The main NP outcomes of interest are raw scores from the working memory/executive function domain scores. Secondary outcomes are cognitive domain-specific scores and global deficit score, with FDR control, as discussed above. We expect to find additive but not interactive effects of HIV and cannabis use on primary NP outcomes. Separate analyses will examine the effect of cannabis on NP outcomes, controlling for peripheral immune indices.

Analyses of brain volumetrics will focus on the hippocampus as the primary outcome. Secondary outcomes will include the caudate, amygdala, putamen, and pre-frontal regions (with FDR corrections). These volumetric analyses will follow a similar pattern to that described for NP outcomes.

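### Hypotheses 1c and 2c: one layer of cross-validation serves feature selection, model comparison and model evaluation, with no outer loop or held-out set specified, so the performance quoted for a chosen model can be optimistic

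*Combined protocol and SAP*

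**What the plan says.** Section F describes the classifier analyses for Hypothesis 1c, and in nearly the same terms for Hypothesis 2c.

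- Resampling, both hypotheses: "All analysis will be conducted with 10-fold cross validation with 10 repeats to ensure the reliability of the results".
- Feature selection, 1c: "The analysis will yield a subset of biomarkers that are most indicative of the effects of cannabis on brain immune activation and inflammation". The 2c paragraph promises a matching subset for cognition and volumetrics.
- Evaluation: models are "evaluated based on sensitivity, specificity, and receiver operator curve (ROC) area under the curve (AUC) F1 analyses".
- Comparison: "Models will be compared using mean misclassification rate and Bayesian information criteria" in 1c, and the same criteria in 2c ("Models will be compared using the mean misclassification rate and Bayesian information criteria").
- The power paragraphs for 1c and 2c add a significance check, "Cross validation of data with randomly permuted labels will be used to identify the significance of model results", and learning curves: "Training and testing errors of cross validated progressively sampled models will be assumed to follow power laws".

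The document names no outer loop, nested cross-validation, held-out set, external validation or optimism correction. The testing errors in the learning curves are those of the cross-validated models, so they are not a separate test set. Four things are not stated: whether feature selection is refitted in each training fold, how many models are compared, which model's figures will be reported, and whether each permutation repeats selection and model comparison.

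**The concern.** Cross-validated error is a noisy estimate of each model's true error. If the model with the lowest estimate is chosen and that same estimate is quoted, the quoted figure is the best of several noisy ones. For estimates Ê₁…Ê_M, E[min Ê_m] ≤ min E[Ê_m], so the error tends to be too low and the AUC too high. Repeating the folds ten times reduces the noise from the random split. It does not remove this bias, because all repeats use the same participants.

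The search could be wide. Section F cites four sources for feature-selection methods (references 92–95) and compares models under two choices of class prior. C3.5 extends the inputs beyond the inflammatory markers to volumetrics, cognition, demographics and clinical data. C1 and C2 expect these classifiers to reveal new mechanisms, so at stake is whether a modest published AUC reflects biology or the search.

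**Working it through.** **Inputs from the document.** Total n is 320, 80 per group. The 70% lumbar puncture completion rate (Power Analysis for Aim 1) leaves 0.70 × 320 = 224 with CSF markers, or 0.70 × 80 = 56 per group. The markers named for 1c number nine: CD4/CD8 ratio, sCD14, sCD163, three monocyte subsets, MCP-1, neopterin and cellularity.

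**The plan's own figures.** The plan gives no AUC, error rate, model count or classifier sample size for 1c or 2c, so there is nothing to reproduce directly. The two sample sizes do agree with its other power figures. Using power ≈ Φ(d√(n/2) − 1.96):
- d = 0.446 at 80 per group: 0.446 × √40 − 1.96 = 0.861, power 0.805.
- d = 0.533 at 56 per group: 0.533 × √28 − 1.96 = 0.860, power 0.805.

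**Simulation.** Assumptions not in the document:
- two balanced classes and independent normal features, 9 or 100 of them;
- univariate ranking followed by ridge linear discriminant analysis;
- 3, 18 or 30 candidate settings (number of features kept, amount of shrinkage);
- 80 data sets per row.

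The setting with the lowest mean misclassification over 10 × 10-fold cross-validation was chosen. Excess = its cross-validated AUC minus the AUC of the same setting, refitted to all data, in 10,000 new subjects. Nested cross-validation used one pass of 10 outer folds, with selection and model choice repeated in each outer training set.

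| Scenario | n | Candidates | Single CV AUC, selection inside folds | True AUC | Excess (SE) | Nested CV AUC | Single CV AUC, selection on all data first |
|---|---|---|---|---|---|---|---|
| Null, 9 features | 320 | 18 | 0.519 | 0.500 | +0.019 (0.005) | 0.499 | 0.552 |
| Null, 9 features | 224 | 18 | 0.520 | 0.500 | +0.020 (0.006) | 0.491 | 0.563 |
| Null, 9 features | 224 | 3 | 0.514 | 0.500 | +0.014 (0.006) | 0.493 | 0.560 |
| Null, 100 features | 320 | 30 | 0.549 | 0.500 | +0.049 (0.005) | 0.512 | 0.666 |
| Null, 100 features | 224 | 30 | 0.553 | 0.501 | +0.052 (0.005) | 0.501 | 0.694 |
| d = 0.3 in 3 of 9 | 224 | 18 | 0.620 | 0.611 | +0.010 (0.005) | 0.594 | 0.635 |
| d = 0.3 in 5 of 100 | 320 | 30 | 0.650 | 0.618 | +0.032 (0.004) | 0.604 | 0.727 |
| d = 0.3 in 5 of 100 | 224 | 30 | 0.635 | 0.590 | +0.045 (0.005) | 0.584 | 0.742 |
| d = 0.6 in 3 of 9 | 320 | 3 | 0.761 | 0.764 | −0.003 (0.003) | 0.758 | 0.761 |

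Excess is computed before rounding.

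- *Selection inside folds.* Outside the strong-signal row, cross-validated error was too low by about 2 to 4 percentage points.
- *Selection on all data first.* In the null 100-feature rows, error was 0.368 and 0.344 against a true value of about 0.50.
- *Nested cross-validation.* It gave 0.491 to 0.512 on null data. With a weak signal it fell slightly below the truth.

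A second null simulation, with 14 settings and 40 data sets per case, gave the same pattern. The best-of-14 AUC was 0.52–0.55 with selection inside the folds. With selection on all data first it was 0.55–0.57 (9 features) and 0.67–0.70 (100 features).

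**Scaling.** On null data (12 settings, 4 × 10-fold, 60 data sets, selection inside folds), scaling within folds versus on all data gave AUC 0.520 v 0.516 (n = 320, 9 features), 0.521 v 0.518 (n = 224, 9 features) and 0.525 v 0.528 (n = 320, 50 features), with SEs of about 0.005–0.008. There is no detectable effect.

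**Permutation.** If selection and model comparison are rerun for each permutation, the null distribution carries the same search advantage as the observed result, and the p-value is protected. If only the final model is refitted, it is not. In neither case does the reported AUC or error change.

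**The case against.** The best defence is that the plan is silent rather than wrong. It says that models will be evaluated and compared. It does not say that one winner will be chosen or that its cross-validated figures will be the final report. A reader might infer that inflated results are certain; the text does not support that. This stands, so the conclusion has to be conditional.

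A reader might also infer from the order of the sentences that features are selected on all data before the folds are drawn. Sentence order is weak evidence. A statement that covers all analysis more naturally puts selection inside the folds. The larger figures therefore describe a possibility the text leaves open, not its likeliest meaning.

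Three further points have force. Scaling does not use the labels, and no large bias from it was shown. With only the nine named markers, the excess is about 0.02. The permuted-label check is aimed at exactly the danger that noise appears to separate the groups.

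What survives is that, even with selection inside the folds, choosing the best model on those folds biases its estimate. No other performance estimate is described, and the permutation check does not supply one. That 1c and 2c are data-driven hypotheses lowers the stakes but does not make an inflated AUC a fair summary.

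**Conclusion.** The concern holds in conditional form. The plan specifies a single cross-validation layer for selecting features and for evaluating and comparing models, and no independent estimate of a chosen model's performance. If a best model is chosen on these folds and its figures are quoted, the likely excess on null data is about 0.02–0.05 AUC with selection refitted inside each fold, falling to about zero with a strong signal and few candidates. If selection were done once on all data, pure noise could give an AUC of about 0.55–0.57 with 9 features and 0.67–0.70 with 100.

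These sizes rest on assumed feature counts, numbers of candidates, a ridge-discriminant classifier and two classes. The direction follows from choosing and quoting on the same folds; the size does not transfer exactly to other methods.

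A reader might infer that BIC should be dropped, or that the main analyses are compromised. Neither follows. BIC is not a cross-validated performance estimate, and nothing here argues against it as a descriptive criterion. Hypotheses 1a, 1b, 2a and 2b use linear models and are unaffected.

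**What to change.** Amend the 1c and 2c paragraphs of section F, and the matching power paragraphs, to state that:

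1. nested cross-validation is used, with feature selection, tuning and model choice (and, as routine practice, scaling) fitted only in the inner training data;
2. sensitivity, specificity, AUC, F1 and misclassification are reported only from the outer 10 × 10-fold loop;
3. each label permutation reruns the entire pipeline, including selection and model choice;
4. the candidate features and models are listed in advance;
5. BIC, if kept, is descriptive.

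No extra participants or data are needed. The cost is more computing time, chiefly from the permutations, and somewhat lower reported AUCs. With a weak signal, nested estimates may fall slightly below the truth (0.594 against 0.611 in one row above).
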